## 3. Background

### 3.1. Overview of Urea Cycle Disorders

[figure not shown]
Urea cycle disorders (UCD) are a group of rare inherited disorders of metabolism caused by deficiencies of any one of eight proteins required for ammonia detoxification and urea synthesis (**Figure 1**) [1]. Collectively, they result in hyperammonemia, which in

its severe or prolonged form may have devastating effects on development and function of the central nervous system [2]. This can manifest soon after birth (neonatal onset) or later in childhood or even adulthood [3]. The variations of severity are most evident in ornithine transcarbamylase deficiency (OTCD) [4], the most common of UCD and the only X-linked disease among them, the rest of which are inherited as autosomal recessive traits. Thus, males with severe OTC deficiency may not survive infancy without vigorous medical intervention and/or liver transplantation [4]. Even with current medical treatment, some evidence suggests that less than 40% of the most severe neonatal cases survive [5]. Males with milder deficiencies may present much later, and females express a range of severity from neonatal onset to being asymptomatic throughout life [4]. Such asymptomatic or mildly affected females represent the largest group within the UCD population, while the more severely affected males and females require the most demanding, intensive, and expensive medical intervention. The classification, abbreviations and estimated prevalence of the various UCD are shown below; as a group, the combined prevalence is approximately 1:35,000 [6].

- N-acetylglutamate synthase (NAGS) deficiency (<1:2,000,000)
- Carbamyl phosphate synthetase I deficiency (CPSD) (1:1,300,000)
- Ornithine transcarbamylase deficiency (OTCD) (1:56,100)
- Argininosuccinate synthase deficiency (ASD, Citrullinemia) (1:250,000)
- Argininosuccinate lyase deficiency (ALD, argininosuccinic aciduria) (1:218,750)
- Arginase (ARG) deficiency (argininemia) (1:950,000)
- Hyperornithinemia, hyperammonemia, homocitrullinuria (HHH) syndrome (or mitochondrial ornithine carrier deficiency-ORNT) (<1:2,000,000)
- Citrullinemia type II (mitochondrial aspartate/glutamate carrier deficiency-CITR) (<1:2,000,000, 1:21,000 in Japanese origin)

**aFigure 1. The Urea Cycle and Enzymes**

**The Urea Cycle**

### 3.2. Impact of Hyperammonemia on the Health of Patients with UCD

Despite significant improvements in medical management following the wider availability of specialized diets, hemodialysis and alternate pathway therapy, infants and children and even adults with urea cycle disorders (UCD) are at high risk of early and recurrent brain damage from hyperammonemia [7, 8]. The insult that the brain suffers from high blood ammonia levels can manifest as cytotoxic brain edema and vascular compromise which frequently leads to intellectual and developmental disabilities [2, 9-11]. Moreover, clinical hyperammonemia recurs at variable intervals increasing the cumulative damage to the brain and the chance of irreversible coma and death during a hyperammonemia episode due to vascular compromise and/or brain herniation. This can, unfortunately, be

the outcome even in those patients whose condition appears to be amenable to conservative management (CM) since the ammonia can “get out of hand” during an intercurrent infection or another stress and cause the demise of the patient [12]. Because hyperammonemia in patients with UCD can occur at any time as a result of catabolic conditions (such as otherwise trivial infections), an increasing number of patients with recurrent hyperammonemia have been undergoing orthotopic liver transplantation as a procedure that “cures” the hyperammonemia [13-15], removing what the patients describe as a “ticking time bomb”. However, liver transplantation is a complicated surgical procedure which carries a significant risk of both mortality and morbidity. Patients, families and their providers are therefore facing a difficult dilemma. Should the patient be managed conservatively with diet, medications, and amino acid supplements or should he/she consider undergoing a liver transplant?

### **3.3. Gap of Evidence with Respect to Best Treatment for Patients with UCD**

There are two major options in the management of severe UCD. One is conventional conservative management and the second is liver transplantation. The goal of conservative management is to prevent or reverse the accumulation of toxic ammonia in the body. This can be accomplished by a combination of the following interventions: 1) reducing protein catabolism by providing a high caloric intake [16]; 2) reducing dietary protein intake, except for required essential amino acids [16]; and 3) providing substrates for alternate pathways of nitrogen excretion (citrulline, arginine, sodium benzoate, phenylacetate, and phenylbutyrate) [17]. In milder cases, the first two nutritional interventions may be sufficient. In severe cases, all these approaches may need to be employed plus the use of hemodialysis to remove nitrogen during life-threatening hyperammonemic crises [18]. Liver transplantation represents a curative approach for the hyperammonemia by replacing the liver with the defective gene with a normal liver [13-15]. This approach, however, carries considerable risks.

#### **3.3.1. Conservative Management and Outcome**

The most effective medical advances in the acute and chronic treatment of UCD are the employment of substrates to promote alternative pathways of waste nitrogen excretion [7, 17]. Sodium benzoate combines with glycine to form hippurate, which can be readily excreted, removing one atom of nitrogen for each molecule of benzoate provided. Sodium phenylacetate combines with glutamine to form phenylacetylglutamine, also readily excreted in the urine and removing two atoms of nitrogen for each molecule of phenylacetate. The same phenylacetate pathway occurs with administration of sodium phenylbutyrate (Buphenyl®) or its prodrug glycerol phenylbutyrate (Ravicti®), which have a much less pungent odor and repugnant taste than phenylacetate itself. Combined therapy with intravenous infusion of glucose, lipid, arginine, and sodium benzoate/sodium phenylacetate (Ammunol®) is now used routinely for treatment of acute hyperammonemia, whereas sodium phenylbutyrate or glycerol phenylbutyrate are commonly used for chronic, long-term oral administration [19, 20]. All of these treatments carry risks of serious side effects. Among patients treated conservatively, many have been reported to succumb to hyperammonemic crises. Most survivors show significant

neurodevelopmental disabilities, the severity of which seems to correlate with the severity of the enzyme deficiency. In a longitudinal study performed by our NIH-funded Rare Diseases Clinical Research Center for Urea Cycle Disorders (UCDC) [21], the proportion of patients with a poor cognitive outcome (IQ/Developmental Quotient <70) was high, ranging from 47-68% in the various UCD. This was observed in patients below and above 4 years of age. Poor cognitive outcome was not fully explained by age of onset (<4 vs. >4 years), peak ammonia level or duration of the initial admission. Thus, we currently do not know what variables are associated with a poorer cognitive outcome in patients with UCD on conservative management, making it difficult to make progress in improving this approach.

### **3.3.2. Liver Transplantation and Outcome**

Liver transplantation for UCD patients was initiated in the early 1990's, before alternate pathway medical therapy was widely available. There were anecdotal case reports of liver transplantation in four of the urea cycle disorders (CPSD, OTCD, ASD, and ALD) [13, 15, 22]. A larger survey of 16 US patients who had received liver transplants from four major transplant centers found that 14 of these cases had survived at least 1-6 years [14]. Their neurological status post-transplantation was in most cases moderately to severely impaired and correlated closely with their condition prior to transplantation. However, the quality of their lives seemed to have improved. Subsequently, to determine if aggressive medical therapy could improve the outcome of severe infantile onset UCD, 5 such cases were monitored at Baylor College of Medicine before and after liver transplantation, including 2 males with OTCD, 2 with CPSD, and one female with OTCD deficiency and intractable hyperammonemia [23]. Three of these infants had serial developmental testing (Griffiths scale) before and after transplantation. It was found that their pre-transplantation overall developmental scales (51, 86, 56) were stabilized after transplantation (70-83, 80-76, 51-47, respectively). Therefore, the authors recommended that early transplantation be considered as the treatment of choice in these severely affected infants.

Most recently, a retrospective analysis of 186 patients with UCD who underwent liver transplantation, [24] showed an increased frequency of liver transplantation for UCD and organic acidemia over the last decade, with 5-year survival rates of 88-99% depending on age. In summary, liver transplantation is now performed frequently to treat UCD and survival seems to have improved over time. However, the outcome of neurocognitive function following liver transplantation is unclear, and it is unknown how it compares to conventional conservative management.

### **3.3.3. The Process of Making UCD Treatment Decisions**

Despite the importance of and complexity surrounding the decision to continue conservative management or consider liver transplant in UCD, no research has been conducted to date on how primary caretakers of pediatric UCD patients make these treatment choices and the issues that influence their decision to pursue one option over another. Some existing research investigating parent decision making in

pediatric treatments has been published in other disease areas such as end-of-life care, cardiac transplantation, lung transplant in patients with cystic fibrosis, and cancer treatment. A 2012 narrative review of the current research on parent decision making about pediatric treatment found that in addition to consulting their provider, most parents consider their child's health status, the perspectives of other members of their community, their prior knowledge, and other personal factors such as emotions and faith when making treatment decisions for their child [25]. Although the findings from these studies can help inform our understanding of the treatment decision-making process among the caretakers of pediatric patients with UCD, the characteristics of this disease group and the risks associated with its treatment options vary in several important ways from other disease areas, effectively limiting the applicability of these previous studies in this population. One of the most critical differences concerns the acuteness and unpredictable nature of severe hyperammonemia episodes, which carry the risk of death or increased neurocognitive dysfunction. Even if a patient's condition appears to be amenable to conservative management, he or she is still susceptible to acute hyperammonemia during incurrent infections or while experiencing other stressors. This "ticking bomb" phenomenon is factored in the treatment decision of patients on whether pursuing liver transplant, thus increasing the need for better research that focuses specifically on the experience of making treatment decisions by the UCD population.

[figure not shown]
### **3.3.4. Gaps in Knowledge to be Addressed by this Project**

In spite of a number of reports (mostly case reports) on UCD, the mortality rate from these disorders remains uncertain. A mortality rate of up to 50% has been quoted in the literature for patients with neonatal onset UCD [22]. However, we have seen much lower mortality rates among the UCDC longitudinal study cohort (23%-34%) but it is unclear whether this discrepancy reflects a real improvement in the management of UCD during the last two decades or whether there exists an ascertainment bias; an effort is underway in the UCDC to remove survivorship bias and reassess the risk of mortality. Conservative management and liver transplantation are associated with mortality and morbidity, due to hyperammonemia in the former, and peri- and post-surgical complications in the latter. It is, therefore, important that we have information to compare survival as well as other outcomes of the two approaches, taking appropriate account of specific disorders ( a type of UCD) and severity (neonatal or late onset). The second major gap in knowledge is with respect to neurocognitive outcome in patients with UCD. While we have both cross-sectional and longitudinal information about patients with UCD managed conservatively [8, 26], we need more information about patients with UCD who underwent liver transplantation. Our collaboration with SPLIT (Studies of Pediatric Liver Transplantation) will enable us to capture all or most patients with UCD who undergo liver transplantation and thus provide a nonbiased evaluation of their outcomes. The third gap in knowledge is regarding the quality of life in patients with UCD, both those managed conservatively and by liver transplantation. Although being on a restrictive diet contributes to a compliance issue, and has been shown to have a detrimental effect on children's quality of life [27], no comparisons with other treatments have been reported. Last but not least, there is a paucity of evidence

about how patients with UCD, their families, and their providers reach a shared decision on which management strategy to choose, how frequently and by what mechanisms these decisions are revisited, and what clinical, social, and/or system level factors influence this decision process. To date, there have been no published studies that examine the experience of providers or patients with UCD and their families in making this critical and difficult treatment decision.

## 4. Study Design and Methods

**Overview:** We will employ a mixed method concurrent study design utilizing quantitative research methods to address our primary outcomes, while simultaneously employing qualitative research methods to obtain information on the UCD patient/family experience when making critical treatment decisions (**Figure 2**).

**Figure 2. Overall Design of the Study**  
 A randomized controlled trial (RCT) in UCDs is not a feasible option to fill an information gap because of the nature of the alternatives and dearth of affected patients. In the quantitative component of this study (**Aim 1**), we, therefore, propose to implement a natural history observational trial, relying on existing historical and concurrently collected registry data to identify our population of interest. This population consists of patients age 18 and under. Many such patients are already enrolled in a Longitudinal (natural history) Study of Urea Cycle Disorders conducted by the Urea Cycle Disorders Consortium (UCDC). This UCDC study captures data regarding survival, neurocognitive status and quality of life. In order to achieve our target sample size and

broaden our subject population, we intend to merge data from the existing UCDC data set with two additional registries maintained by: 1) the Studies of Pediatric Liver Transplantation (SPLIT) Research Group, housed at the EMMES Corporation and 2) National Urea Cycle Disorders Foundation (NUCDF) patient stakeholders. To study the two UCD patient cohorts, one managed conservatively and the other treated by liver transplantation, we will use covariate balanced propensity score matching to greatly reduce bias in this non-randomized study. Propensity score matching is widely recognized as a best practice alternative when an RCT is not feasible.

In the qualitative component of this study (**Aims 2 and 3**), we intend to enroll a representative sample of pediatric patient caretakers (guided by referrals from the NUCDF) and medical providers, including the treating physician and other clinicians on the team (guided by referrals from UCDC site coordinators) to participate in semi-structured interviews that will explore how decisions about UCD treatment are being made. Patient caretakers will also be asked to take part in focus groups to provide feedback on themes that emerged from the semi-structured interviews and to discuss effective strategies for the dissemination of evidence-based information obtained in this study.

#### 4.1. Inclusion Criteria

##### **Aim 1 (UCD patients):**

- Age 18 and under
- Diagnosed with the following Neonatal-type urea cycle disorders:
  - o CPSD, OTCD, ASD or ALD, as defined as follows:
    - Diagnosis of CPS I deficiency, defined as decreased (less than 20 % of control) CPS I enzyme activity in liver, and/or an identified pathogenic mutation, and/or hyperammonemia and first-degree relative meets at least one of the criteria for CPS I deficiency
    - Diagnosis of OTC deficiency, defined as the identification of a pathogenic mutation, and/or less than 20% of control of OTC activity in the liver, and/or elevated urinary orotate (greater than 20 uM/mM) in a random urine sample or after allopurinol challenge test, and/or hyperammonemia and first-degree relative meets at least one of the criteria for OTC deficiency
    - Diagnosis of AS deficiency (Citrullinemia), defined as a greater than or equal to 10-fold elevation of citrulline in plasma, and/or decreased (less than 20% of control) AS enzyme activity in cultured skin fibroblasts or other appropriate tissue, and/or identification of a pathogenic mutation in the AS gene, and/or hyperammonemia and first-degree relative meets at least one of the criteria for AS Deficiency
    - Diagnosis of AL deficiency (Argininosuccinic Aciduria, ASA), defined as the presence of argininosuccinic acid in the blood or urine, and/or decreased (less than 20% of control) AL enzyme activity in cultured skin fibroblasts or other appropriate tissue, and/or identification of a pathogenic mutation in the AL gene, and/or hyperammonemia and first-degree relative meets at least one of the criteria for AL Deficiency
  - Willing to participate in at least 1 neurocognitive assessment and 1 quality of life assessment
  - Permit access to medical records and medical providers

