## 1.1. Overview

Urea cycle disorders (UCD) are genetic disorders caused by the liver's inability to break down ammonia from proteins; ammonia then accumulates and is toxic to the brain. UCD cause brain damage, intellectual, developmental disabilities, and even death. Medical treatment involves special diet low in protein, drugs that help metabolize ammonia and amino acid supplements (conservative management). However, many patients and families choose liver transplantation rather than conservative treatment; both alternatives are effective in reducing or normalizing blood ammonia. While liver transplantation eliminates the ammonia problem, conservative management does so only temporarily and in many patients, blood ammonia can rise during an infection or other stress. The long-term objective of this study is to help patients make decisions about management alternatives (medical vs. liver transplantation) by providing them with scientific information that is currently lacking.

The questions that will be addressed are:

1. What is the disease's risk of mortality and illness in each treatment approach?
2. What can parents expect in terms of the neurocognitive development of their child and his/her school performance?
3. What are the expected effects of each treatment on short-term and long-term quality of life?
4. What factors do primary caretakers (typically parents) consider when making the decision to pursue liver transplantation or continue conservative management for their child with UCD?

This research will have two components. In one, we will use statistical methods to compare survival, illness, psychological testing for IQ, executive function, memory, behaviors, and quality of life among patients that choose conservative management and those who have chosen liver transplantation. Some of this information is already being collected by the Urea Cycle Disorders Consortium (UCDC) in 14 metabolic clinics (11 of them in the US) as part of its longitudinal natural history study. To ensure that the information we analyze is representative of the UCD patient population in the US, we will also obtain data from the Studies of Pediatric Liver Transplantation (SPLIT) registry, which collects information about children who undergo liver transplantation for many different diseases (including UCD), and from the National Urea Cycle Disorders Foundation (NUCDF) a patient advocacy group for patients with UCD.

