## 4.3. Recruitment of Participants

**Aim 1:** De-identified data from the Longitudinal (natural history) Study (LS) of the Urea Cycle Disorders (UCD) will be supplemented with data from subjects identified from two sources: the Studies of Pediatric Liver Transplantation (SPLIT) Research Group and the National Urea Cycle Disorders Foundation (NUCDF).

Longitudinal Study participants will not be recruited to participate in this study, but their data used for this analysis, as is permissible per the LS consent form.

By agreement, when this project is implemented, SPLIT will contact its respective transplant centers to describe the study and its eligibility criteria indicating the number and descriptive characteristics of eligibility based on SPLIT anonymized records asking study staff to contact eligible patients and provide general recruitment materials. NUCDF will also distribute recruitment materials and directly enroll eligible participants to the study. In all cases, interested patients will contact one of the study sites to express their interest in participating in the study.

Enrollment in the UCDC LS will be offered to any patient not already enrolled, so that they can take advantage of the rare disease protocol to capture laboratory data, neurocognitive function and quality of life information, using the resources already in place through the UCDC. Participants interested in enrolling in the LS will be put in

touch with the study coordinator and PI at the nearest (or preferred) UCDC site. The PCORI site coordinator will work closely with LS coordinators to ensure that contact with interested participants is not delayed. We anticipate that a large proportion will agree to participate in the PCORI study, which will require only two visits for neuropsychological testing and self-reported quality of life questionnaire.

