### 8.4. Written Informed Consent

**Aim 1:** Written informed consent will be obtained from each participant before any study-specific procedures or assessments are done and after the aims, methods, anticipated benefits, and potential hazards are explained. The participant's willingness to participate in the study will be documented in writing in a consent form, which will be signed by the participant with the date of that signature indicated. The investigator will keep the original consent forms and signed copies will be given to the participants. It will also be explained to the participants that they are free to refuse entry into the study

and free to withdraw from the study at any time without prejudice to future treatment. Written and/or oral information about the study in a language understandable by the participant will be given to all participants.

**Aim 2 & 3:** No written informed consent will be obtained for either interview or focus group participants. Instead, prospective subjects will be provided an information sheet about the study, as described in 8.5.

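### The Aim 1 survival analysis in section 6.2 sets no time origin, no delayed entry and no rule for time before transplant, although patients enter by different routes

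*Combined protocol and SAP*

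**What the plan says.** Section 6.2 is the whole survival plan. Survival times are compared by log-rank within strata of the covariate-balancing propensity score (CBPS). Cox models by treatment then adjust for that score or stratify on it. No time zero, entry time, time-dependent transplant term, landmark, or censoring at a later transplant is given. The nearest text is a balancing covariate: time from birth to transplant, or to an index date that is not defined.

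The same section describes the propensity as that of passing from conservative care to transplant. Table 2 (section 6.1) gives surgery age as 11.7 months (1.5-186) and projects 92 transplanted and 93 conservatively managed children.

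Section 4.3 describes different entry routes. For the Longitudinal Study (LS): "Longitudinal Study participants will not be recruited to participate in this study, but their data used for this analysis". For SPLIT and NUCDF: "In all cases, interested patients will contact one of the study sites to express their interest in participating in the study". Section 8.4 adds "Written informed consent will be obtained from each participant before any study-specific procedures or assessments are done", and section 4.1 requires patients to be "Willing to participate in at least 1 neurocognitive assessment and 1 quality of life assessment".

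On SPLIT data, section 1.1 says "we will also obtain data from the Studies of Pediatric Liver Transplantation (SPLIT) registry" and section 4 says "we intend to merge data from the existing UCDC data set with two additional registries maintained by". Section 3.3.4 expects SPLIT to "enable us to capture all or most patients with UCD who undergo liver transplantation and thus provide a nonbiased evaluation of their outcomes". Section 4.3 has SPLIT approach its centers, "indicating the number and descriptive characteristics of eligibility based on SPLIT anonymized records", so that staff there can contact patients.

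Section 3.3.4 also acknowledges possible survivorship bias in LS mortality. Section 6.2 has no step for it.

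**The concern.** Two kinds of guaranteed survival can enter the comparison. A child recruited years after transplant or diagnosis must have lived until recruitment. A transplanted child must have lived on conservative management until surgery. If that time is counted as time at risk, or credited to the transplant arm, the arms can differ with no treatment effect, or a real effect can be hidden. CBPS balances measured covariates. It cannot restore children who died before they could be recruited or transplanted.

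No route is described for a SPLIT or NUCDF child who died before contacting a site. The SPLIT passages leave unclear whether such deaths are counted through registry records.

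Survival is one of three outcomes in the primary objective, and mortality risk is the first question listed in section 1.1. The results are to be given to families choosing between the two treatments.

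**Working it through.** The plan gives no figure for this bias, so there is none to reproduce. The calculations are illustrations with equal true hazards (true ratio 1.00).

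**1. Late entry ignored, clock at transplant or index date.** From the documents: mortality 28% (section 6.2, no time horizon) and arms of 92 and 93 (section 6.1). Assumed: 28% is reached at 10 years in both arms with constant hazard. Recruited children enter uniformly over years 0-10 if alive and are followed for 3 years or to year 10. LS children enter at year 0 and are followed to year 10.

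- Hazard: λ = -ln(0.72)/10 = 0.03285 per year.
- LS child: expected deaths 0.28; person-years 0.28/λ = 8.523.
- Recruited child, deaths after entry: [(1-e^(-3λ))(1-e^(-7λ)) + e^(-7λ) - e^(-10λ) - 3λe^(-10λ)]/0.28 = (0.09385×0.20543 + 0.79457 - 0.72 - 0.07096)/0.28 = 0.0818.
- Recruited child, person-years after entry: 0.0818/λ = 2.489. Mean entry time: 1/λ - 10×0.72/0.28 = 4.727. Person-years from the origin: 7.216.

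With 50% of the transplant arm and 0% of the conservative arm recruited:
- Entry ignored: (0.5×0.28 + 0.5×0.0818)/(0.5×8.523 + 0.5×7.216) = 0.1809/7.870 = 0.02298. Ratio 0.02298/0.03285 = 0.70.
- Delayed entry: 0.1809/(0.5×8.523 + 0.5×2.489) = 0.1809/5.506 = 0.03285. Ratio 1.00.

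If LS children instead enter uniformly over years 0-5 if alive, each contributes 1 - 5λ×0.72/(1-e^(-5λ)) = 0.2192 deaths, 6.674 person-years after entry, a mean entry time of 2.432, and 9.106 person-years from the origin.

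| Recruited share, transplant/conservative | LS entry at 0 | LS entry over 0-5 | Delayed entry |
|---|---|---|---|
| 25%/0% | 0.86 | 0.89 | 1.00 |
| 50%/0% | 0.70 | 0.77 | 1.00 |
| 50%/25% | 0.82 | 0.86 | 1.00 |
| 50%/50% | 1.00 | 1.00 | 1.00 |
| 25%/50% | 1.22 | 1.16 | 1.00 |

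Simulations of the same set-up agree to within about 0.01, with extremes of 0.70 and 1.23.

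**2. Clock at birth, arms fixed by eventual treatment.** Assumed: 28% mortality by age 18, with 5%, 10% or 20% in year 1. Half the children have a planned transplant age, lognormal with median 11.7 months, truncated to 1.5-186 (reading Table 2 as median and range), log-SD 0.8 or 1.2. LS entry is uniform in year 1, with delayed entry already applied. The estimator is the age-stratified Mantel-Haenszel rate ratio, Σ(d₁p₀/T)/Σ(d₀p₁/T), where d is deaths, p person-time and T = p₀ + p₁.
- Ever versus never transplanted: 0.78-0.82, 0.68-0.72 and 0.45-0.46 at first-year mortality of 5%, 10% and 20%.
- Transplant as time-dependent exposure: about 0.99-1.02.
- Clock at transplant, with an age-matched index date drawn from children not yet transplanted: 0.99-1.01. Drawn only from never-transplanted children: 0.86-0.97.

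**3. Handling of SPLIT records.** With half the transplant arm from SPLIT:
- Deceased SPLIT records added to delayed-entry volunteers: 1.37-1.40.
- All SPLIT records, living and dead: 1.00.
- Volunteers entered at SPLIT registration (assumed at transplant) instead of consent: 0.56-0.67.

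**4. Deaths.** If 28% of 185 were observed: 0.28×185 = 52. At 50%/0%: 92×0.1809 + 93×0.28 = 42.7. With LS entry over years 0-5: 92×(0.5×0.2192 + 0.5×0.0818) + 93×0.2192 = 34.2. Recruits are alive at entry, so their deaths count with or without delayed entry.

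**The case against.** The best counter-argument is that this is an omission, and that nothing in section 6.2 commits the analyst to a biased clock. Pairing transplant with an index date suggests that a control clock was contemplated. If it were the clock and were well defined, the birth-clock ratios would not apply. That much stands. But the index date is undefined, appears only as a balancing covariate, and would leave late entry unhandled. The intent-to-treat statement in section 5.6 does not help, because nothing assigns treatment at a time zero.

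Some stronger readings are tempting but unsupported:
- A reader might infer from section 4.3 that SPLIT records serve only to describe eligibility, so deceased children are certainly excluded. The section does not say so, and it also speaks of adding data on subjects identified through SPLIT and NUCDF. The passages are unclear together; they do not establish exclusion.
- A reader might infer that arms are fixed by eventual treatment. The 92/93 split is a sample-size projection, not an analysis rule.
- A reader might quote an inflated false-positive rate. An overall log-rank test ignoring entry rejects in 10-19% of simulated studies at 50%/0%, and in 6-9% at the other unequal mixes. The high figure needs the extreme mix, 28% mortality in both arms, and an overall test, whereas the plan's log-rank is within strata. At constant hazard, 28% at ten years implies 0.72^0.5 = 84.9% five-year survival, below the 88-99% cited for transplant in section 3.3.2. With 95% five-year survival the 50%/0% rejection rate falls to 6.1-8.3%. The rate ratios depend much less on this assumption.
- A reader might assume that the bias favors transplant. With more recruits in the conservative arm it runs the other way.

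**Conclusion.** The point holds and should be fixed before any survival result is produced. As it stands, section 6.2 does not define the survival comparison well enough to exclude bias from late entry or pre-transplant time, and the design gives reason to expect both. Size and direction cannot be estimated from the documents. The ratios of about 0.70 to 1.23 rest on assumed source mixes, entry times and a constant hazard. Those of about 0.45 to 0.82 also require arms fixed from birth by eventual treatment, which the plan does not state. LS entry rules are not in these documents; section 4.4 says only that LS enrollment began in 2006. The firm conclusions are that the rules are missing, that CBPS cannot supply them, and that standard methods bring the ratio back to about 1.00 in these illustrations. The passages on SPLIT data must be reconciled.

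**What to change.** 1. In section 6.2, use age as the time scale with transplant as a time-dependent exposure in the Cox model. Alternatively, start the clock at transplant and at a defined, age-matched index date for children alive, under observation and not yet transplanted, censored at any later transplant. The second option permits Kaplan-Meier curves and CBPS covariates fixed at one date. It needs a robust variance, because a child can appear in both arms, and a check for informative censoring, because the risk factors that feed the propensity for transplant may also predict death.
2. Use delayed entry in Kaplan-Meier, log-rank and Cox analyses: study consent for recruited patients, LS enrollment for LS members.
3. Reconcile sections 1.1, 3.3.4 and 4 with section 4.3. If SPLIT supplies records, include all eligible SPLIT patients, living and dead, from registration; never add deceased records alone to volunteers. Otherwise rely on delayed entry.
4. Report source per arm, and repeat the survival comparison without consent-recruited patients as a sensitivity analysis.
5. Restate expected deaths and mortality power for the resulting analysis set.

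The cost is protocol wording plus an entry date and a transplant or index date per patient; section 4.5 already asks for careful recording of historical dates. Downsides are less person-time and small early risk sets. Registry-only records may lack CBPS covariates, and using non-volunteers' records needs SPLIT and IRB agreement. A duplicate check is needed, with a stated method, because LS data are de-identified and SPLIT records anonymized. Healthy-volunteer bias remains. Delayed entry itself loses no deaths among patients alive at entry; any shortfall against 52 comes from how and when patients are recruited.
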